## **Sample Size**

A post hoc power analysis (one-way ANOVA; Cohen's  $f = 0.25$ , alpha 0.05, three groups,  $n = 197$ ) yielded power of 0.96.

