## Objectives

**Primary Objective:** To compare binocular uncorrected distance, intermediate, and near visual acuity and patient satisfaction at 6 months among monofocal, enhanced monofocal, and EDOF IOLs.

**Secondary Objectives:** To compare monocular and binocular corrected acuities, refraction, defocus curve performance, and halo/glare symptoms among the three IOL groups.

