# **Statistical Analysis Plan (SAP)**

## **Analysis Population**

All eligible patients completing 6-month follow-up were included. Both eyes contributed to outcomes; inter-eye correlation was addressed using GEE for selected analyses.

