## **Comparative Analyses**

- Kruskal–Wallis tests with Dunn–Bonferroni post hoc comparisons for non-normally distributed continuous outcomes.
- One-way ANOVA with Tukey HSD for key binocular outcomes when appropriate.
- Chi-square or Fisher’s exact tests for categorical variables.
- GEE model with exchangeable correlation structure for binocular UIVA to account for within-subject correlation.

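### The one power figure covers only the global three-lens ANOVA (about 0.89 on its own inputs, not 0.96); power for the lens-versus-lens tests is unstated and depends on group sizes and the pattern of means

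*Combined protocol and SAP*

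**What the plan says.** The Sample Size section of the protocol consists of one statement: "A post hoc power analysis (one-way ANOVA; Cohen's" f of 0.25, "alpha 0.05, three groups" and n = 197, which "yielded power of 0.96". It gives no other power or precision figure.

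The primary objective compares binocular uncorrected acuity at three distances and "patient satisfaction at 6 months among monofocal, enhanced monofocal, and EDOF IOLs". No lens pair is named as the main contrast.

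The SAP, under Comparative Analyses, provides two routes to lens-versus-lens conclusions: "Kruskal–Wallis tests with Dunn–Bonferroni post hoc comparisons for non-normally distributed continuous outcomes", and "One-way ANOVA with Tukey HSD for key binocular outcomes when appropriate". It also specifies a GEE model for binocular UIVA.

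Group sizes, standard deviations and an expected pattern of means appear nowhere. The analysis set is completers ("All eligible patients completing 6-month follow-up were included"), so no dropout adjustment is needed when 197 is used as the analysed number of patients.

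**The concern.** A significant one-way ANOVA says that the three lens means are not all equal. It does not say whether the enhanced monofocal lens differs from the monofocal lens, or the EDOF lens from the enhanced monofocal. Those statements rest on the adjusted pairwise tests, whose power can be very different from that of the global test at the same f.

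The data are already collected, so the power figure cannot influence enrolment. Its remaining use is to help a reader interpret the results, above all the non-significant ones. There are six primary outcomes (three acuities and three satisfaction scores), each with three lens pairs. Beside a stated power of 0.96, a non-significant pair may be taken as a well-powered finding of no difference, when the study may have had little chance of detecting a real difference for that pair.

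**Working it through.** **Inputs.** From the Sample Size section: f = 0.25, alpha = 0.05, k = 3, N = 197 (read as patients), stated power 0.96. From Comparative Analyses: Tukey HSD, and Dunn–Bonferroni over three pairs (0.05/3 = 0.0167 per pair). Assumed, because the documents do not say: equal groups of 197/3 = 65.67, and normal data with a common SD of 1.

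**Step 1: the plan's own figure.** Noncentrality λ = N f² = 197 × 0.0625 = 12.31, with 2 and 194 degrees of freedom. The noncentral F gives power 0.887, so 0.96 is not reproduced. Other readings also miss it: alpha 0.10 gives 0.937, two groups 0.937, 394 eyes 0.996, and 197 per group more than 0.999. Reaching 0.96 needs f of about 0.29 at N = 197, or N of about 264 at f = 0.25.

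**Step 2: what f implies for the pairs.** Let a and b be the two gaps between the ordered means, in SD units. With equal groups, f² = 2(a² + ab + b²)/9, so a² + ab + b² = 9 × 0.0625/2 = 0.281.
- Evenly spaced (a = b): 3a² = 0.281, so a = 0.306 for neighbouring pairs and 0.612 for the extreme pair.
- One lens differs (b = 0): a = 0.530 for both truly different pairs.

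These are the two ends of the possible patterns. The smaller gap is largest under even spacing (0.306), and the extreme difference always lies between 0.530 and 0.612. Here, neighbouring means adjacent in the order of the means. That this order runs monofocal, enhanced monofocal, EDOF is itself an assumption.

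**Step 3: pairwise power.** The Tukey critical value is the studentized range quantile divided by √2, 2.362. Dunn–Bonferroni uses z = 2.394. Tukey power is from the noncentral t with noncentrality d/√(2/65.67); Dunn power is simulated on normal data with groups of 66/66/65.

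| Pattern | Pair | d | Tukey | Dunn–Bonferroni |
|---|---|---|---|---|
| Evenly spaced | each neighbouring | 0.306 | 27% | 22–23% |
| Evenly spaced | extreme | 0.612 | 87% | 83–84% |
| One lens differs | each truly different | 0.530 | 75% | 70% |

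Under even spacing, the chance that all three pairs are significant with Tukey is about 3%. The chance that at least one is significant is about 88%, close to the global power.

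**Step 4: unequal groups.** With evenly spaced means scaled to f = 0.25, splits such as 97/50/50, 50/97/50, 100/60/37, 90/60/47 and 60/90/47 put neighbouring-pair power at about 18–38%. These splits are illustrative, and more lopsided ones could fall outside that range.

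**Step 5: detectable difference per pair at 80% power.** d = (critical value + 0.842) × √(2/65.67), where √(2/65.67) = 0.1745.
- Tukey: (2.362 + 0.842) × 0.1745 = 0.559.
- Dunn–Bonferroni: (2.394 + 0.842) × 0.1745 = 0.565. Allowing for the 0.955 efficiency of rank tests under normality, 0.565/√0.955 = 0.578.

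The Dunn value is approximate. Linear interpolation between the simulated 70% at 0.530 and 83% at 0.612 gives 0.530 + 0.082 × 10/13 = 0.593, slightly above the formula.

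**The case against.** The strongest reply is that nothing is mislabelled. The sentence openly names a one-way ANOVA, the objective is a comparison "among monofocal, enhanced monofocal, and EDOF IOLs" with no prespecified pair, and the global test is the first step of both routes in the SAP. This stands in part: the plan does not pass the figure off as pairwise power. The SAP nevertheless goes on to pairwise tests, and gives the reader nothing on what those can detect.

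A reader might infer that the study has about 25% power for monofocal versus enhanced monofocal. The documents do not support that. It requires equal groups, evenly spaced means and a particular ordering of the lenses, none of which is stated. If one lens stands apart from two equal ones, each truly different pair has about 70–75% power, and a non-significant result would not be the expected one.

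A reader might also infer that pairwise power is far below global power for every pair. It is not: the extreme pair under even spacing, at 87% with Tukey, is within 2 points of the correct global value of 0.887. Nor should pairwise shortfalls be measured against 0.96, since about 7 points of any such gap (0.96 − 0.887 = 0.073) come from the separate error in the global figure.

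Three further limits stand. The SAP also gives binocular UIVA a GEE model, and the pairwise figures here do not describe it. No passage announces that non-significant pairs will be called equal, so the misreading is a risk and not a stated intention. Finally, one post hoc power figure in place of another adds little by itself; confidence intervals for the pairwise differences are more informative, and the fix includes them.

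**Conclusion.** The point holds in a limited form. The only power figure in the plan describes the global test, and from its own inputs it is about 0.89. The tests that decide which lens differs from which have no stated power or detectable difference.

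The size of the shortfall depends on what the documents leave out. What holds for any pattern of means, given f = 0.25, equal groups, normal data and Tukey HSD, is that the closest pair has at most about 27% power and no pair exceeds about 87%. Even at f = 0.29, where the global power would be 0.96, a neighbouring pair under even spacing would have only about 37%. The issue therefore survives correction of the global figure.

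The consequence is for interpretation. The study cannot read a non-significant lens pair as equality on the strength of the quoted power. The point does not show that the study is too small for its stated aim, or that any particular pair is underpowered.

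**What to change.** **Sample Size section.** Restate the ANOVA power as about 0.89 for the stated inputs, or give the inputs that produce 0.96, and say that it covers the global test only. Add the number of patients per lens. Give the smallest pairwise difference detectable with 80% power at those group sizes; at about 66 per lens this is d of about 0.56 with Tukey and 0.56–0.58 by formula with Dunn–Bonferroni (nearer 0.59 by simulation). Express it in logMAR and in points of the 0–10 satisfaction scale as well.

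**Comparative Analyses section of the SAP.** Report a multiplicity-adjusted confidence interval for each lens pair on each primary outcome: Tukey simultaneous intervals on the ANOVA route, and Bonferroni-adjusted intervals for the location shift on the rank route (1 − 0.05/3, or 98.3% per pair). State that a non-significant pair is not evidence that the lenses are equal, and that the interval shows which differences remain possible.

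**Cost.** One recalculation, one extra set of intervals and a few sentences; no further patients. The downside is that the stated power becomes less favourable.

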## **Significance Threshold**

Two-tailed  $p \leq 0.05$  considered statistically significant.

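### The stated power of 0.96 does not follow from the inputs printed beside it, which give 0.89; the power or an input needs correcting

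*Combined protocol and SAP*

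**What the plan says.** The protocol's Sample Size section is one sentence. It describes "A post hoc power analysis (one-way ANOVA; Cohen's" f set at 0.25, then "alpha 0.05, three groups" and n = 197, and reports that the calculation "yielded power of 0.96". No group sizes, formula or software are given for it, and there is no other power or sample-size figure in the documents.

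Three parts of the SAP bear on how the inputs should be read:

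- **Comparative Analyses** plans "One-way ANOVA with Tukey HSD for key binocular outcomes when appropriate", so the omnibus F test is one of the planned tests.
- **Significance Threshold** uses a two-tailed p of 0.05 or less, which agrees with the alpha in the power sentence.
- **Analysis Population** says "All eligible patients completing 6-month follow-up were included", so 197 needs no allowance for dropout.

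**The concern.** The sentence supplies everything that a one-way ANOVA power calculation needs: the test, the effect size, alpha, the number of groups and the sample size. The result can therefore be checked directly, and it comes out about 7 percentage points below the printed value. Rounding cannot account for a gap of that size.

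What is at stake is the accuracy of the only statement about power in the documents. If the inputs are right, the chance of missing an effect of f = 0.25 with the omnibus test is understated by a factor of nearly three. If the power is right, one of the inputs is wrong, and the effect size that the study is said to be able to detect is probably misreported. In either case the sentence cannot be reproduced.

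**Working it through.** **Inputs, all from the Sample Size section:** one-way ANOVA; f = 0.25; alpha = 0.05; k = 3 groups; n = 197, read as the total number of patients. Stated result: 0.96.

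**Attempt to reproduce the stated figure**

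1. Degrees of freedom: k − 1 = 2 and N − k = 197 − 3 = 194.
2. Noncentrality: N × f² = 197 × 0.25² = 197 × 0.0625 = 12.31.
3. Critical value: the 95th percentile of the central F(2, 194), which is 3.04.
4. Power: the probability that a noncentral F(2, 194; 12.31) exceeds 3.04, which is 0.8865.

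A standard library routine for ANOVA power returns the same 0.8865. The large-sample chi-square approximation gives 0.891. The stated 0.96 is not reproduced.

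**Size of the discrepancy**

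- Power: 0.96 − 0.887 = 0.073.
- Type II error at f = 0.25: 1 − 0.887 = 0.113, against 1 − 0.96 = 0.04. The ratio is 0.113 / 0.04 = 2.8.

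**Does another reading of the inputs give 0.96?** Each row changes one item and keeps the rest.

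| Reading | Power |
|---|---|
| 198 patients (66 per group) | 0.888 |
| f derived from eta-squared of 0.0625 (f = 0.258) | 0.906 |
| Two groups instead of three | 0.937 |
| Alpha 0.10 | 0.937 |
| Both eyes counted (2 × 197 = 394) | 0.996 |
| 197 per group (3 × 197 = 591) | 0.9999 |

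None comes within two percentage points of 0.96.

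**What would give 0.96, changing one input at a time**

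- N: 263 gives 0.9594 and 264 gives 0.9601, so about 264 patients.
- f: 0.29 with N = 197 (noncentrality 197 × 0.0841 = 16.57) gives 0.960.
- Alpha: about 0.15.

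None of these values appears in the documents.

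**The case against.** **The figure carries no weight in the design.** Study Design describes a retrospective case series, and the power calculation is labelled post hoc. It did not determine how many patients were included, and no estimate, test, threshold or analysis set depends on it. The corrected value still exceeds 0.80. All of this stands, and it is why the point is a reporting correction and not a design flaw.

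**The power may be right and an input wrong.** With f of about 0.29 the printed 0.96 is reproduced at 197 patients, and the documents cannot settle which number was misreported. This stands too, and the fix allows for it. The 11% type II error applies only if f = 0.25 is the intended effect size.

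**Some constructions do land near 0.96.**

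- A one-sided pairwise z-test on the largest contrast compatible with f = 0.25 (0.25 × √6 = 0.61 SD, 197/3 = 65.7 per group) gives 0.969.
- Two groups combined with alpha 0.10 give 0.968.
- An assumed 45/10/45 percent split, with f defined under equal weights and the small group holding the middle mean, gives 0.961.

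None of these is the calculation described. The section names a three-group one-way ANOVA at alpha 0.05, and the SAP tests two-tailed. The third also depends on where the means fall: other placements within the same split give 0.919 or 0.496.

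**Stronger readings that a reader might infer.** The documents do not support these:

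- *That the study is underpowered.* For a single omnibus test at f = 0.25, 0.89 does not show that.
- *That unequal lens groups must lower the power further.* No group sizes are given. If f is defined with group-size weights, the noncentrality is N × f² for any allocation and the power stays at 0.887. If f is defined with equal weights, imbalance can move the power either way.
- *That the power should be judged at an alpha divided across the primary outcomes.* The plan specifies no such division. Multiplicity is a separate question and is not evidence of an arithmetic error.
- *That the protocol uses 0.96 to claim adequacy or to support null findings.* It reports the number and draws no conclusion from it.

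**Conclusion.** The point holds as an arithmetic inconsistency. The inputs in the Sample Size section give power of 0.89, not 0.96, and at f = 0.25 the type II error is about 11%, not 4%. This rests on two readings: that 197 is the total number of patients, and that the calculation was the standard omnibus F test with noncentrality N × f². The first is secure, because 197 per group or a count of eyes would give more than 0.99. The second is what the section names.

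The documents do not show which number is wrong. The seriousness is moderate: the sentence should be corrected, but the planned analyses are unaffected and the study's power for one test remains above the usual benchmark.

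**What to change.** Make the Sample Size sentence reproducible in one of two ways:

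1. If the printed inputs are those that were used, restate the power as 0.89 and say that it refers to a single omnibus test.
2. If a different input was used, for example f of about 0.29, correct that input and keep 0.96.

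The original power calculation should show which applies. The cost is one sentence, with no new data and no change to the analyses. Under the first option the reported power becomes less favourable; under the second, the effect size to which it refers becomes larger.

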## **Ethics**

The study adhered to the Declaration of Helsinki and was approved by the Sakarya University Faculty of Medicine Non-Interventional Ethics Committee (Approval 2022/294). Written informed consent was obtained.

## **Data Sharing**

Individual participant data will not be shared.

# **Statistical Analysis Plan (SAP)**

## **Analysis Population**

All eligible patients completing 6-month follow-up were included. Both eyes contributed to outcomes; inter-eye correlation was addressed using GEE for selected analyses.

## **Descriptive Statistics**

Continuous variables summarized as mean  $\pm$ SD. Categorical variables summarized as counts and percentages.

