### Primary Outcomes (6 months):

- Binocular UDVA, UIVA, UNVA (logMAR).
- Patient satisfaction scores for distance, intermediate, and near spectacle-free vision (0–10 scale).

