### Secondary Outcomes (6 months):

- Monocular UDVA, UIVA, UNVA (logMAR).
- Monocular and binocular CDVA, CIVA, CNVA.
- Manifest and objective spherical equivalent refraction.
- Binocular defocus curve performance.

- Halo and glare scores (NEI-RQL-42 items 17 and 38; 0–100 scale).

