## **Normality Testing**

Kolmogorov–Smirnov and Shapiro–Wilk tests assessed normality.

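### Non-normal outcomes are to be tested by ranks but summarised only by mean and SD, so the printed summary does not match the test and can, if lens groups differ in shape, point the other way

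*Combined protocol and SAP*

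**What the plan says.** The SAP, Descriptive Statistics, gives a single rule: "Continuous variables summarized as mean" with SD. It makes no exception for skewed or bounded variables.

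The next two sections bring in a different scale of comparison. Under Normality Testing, Kolmogorov–Smirnov and "Shapiro–Wilk tests assessed normality". Under Comparative Analyses, the plan lists "Kruskal–Wallis tests with Dunn–Bonferroni post hoc comparisons for non-normally distributed continuous outcomes", and separately "One-way ANOVA with Tukey HSD for key binocular outcomes when appropriate". It does not say which named outcomes take which route, apart from a GEE for binocular UIVA.

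The protocol's primary outcomes are three binocular uncorrected acuities and three satisfaction scores on a 0–10 scale. The secondary outcomes include halo and glare scores on a 0–100 scale.

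Neither document mentions a median, IQR, mean rank, Hodges–Lehmann shift or probability of superiority.

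**The concern.** Kruskal–Wallis and Dunn's test ask whether patients with one lens tend to score higher than patients with another. They do not compare means. For an outcome on that route, the planned table would show means, SDs and a p-value, and the p-value would not be about those means. Nothing in the table would estimate what was tested.

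Usually this only makes the result harder to interpret. On a bounded score it can mislead. Suppose one lens leaves most patients at the top of the scale and a minority clearly unhappy, while another leaves nearly everyone at 8 or 9. The first can rank higher and still have the lower mean. A reader who takes direction from the means would then credit the wrong lens with the significant difference. Three of the six primary outcomes are bounded scores of this kind. The Data Sharing section says individual data will not be released, so readers could not check for themselves.

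**Working it through.** **The plan's own figure.** The only computed figure in the documents is the post hoc ANOVA power in Sample Size. It says nothing about how results are summarised, and this point does not use it. For completeness, f = 0.25, N = 197, three groups and alpha 0.05 give λ = 197 × 0.25² = 12.31 and power 0.887, not the stated 0.96. That is a separate matter.

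**Inputs.** N = 197 comes from Sample Size and the 0–10 scale from Primary Outcomes. Group sizes are not given, so 66/66/65 is assumed. Whole-number scores and all score distributions below are also assumed, because the documents hold no outcome data.

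**Step 1: can the direction reverse at this size and scale?** Take one constructed dataset:
- Lens A (66): 30 tens, 20 nines, 5 eights, 5 threes, 6 ones.
- Lens B (66): 8 tens, 22 nines, 28 eights, 8 sevens.
- Lens C (65): 6 tens, 20 nines, 29 eights, 10 sevens.

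Means: A = 541/66 = 8.20 (SD 2.93); B = 558/66 = 8.45 (SD 0.86); C = 542/65 = 8.34 (SD 0.85). Lens A looks worst.

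Pooled midranks for scores 1, 3, 7, 8, 9, 10 are 3.5, 9, 20.5, 60.5, 122.5, 175.5. Mean ranks: A = 8083.5/66 = 122.5; B = 5957/66 = 90.3; C = 5462.5/65 = 84.0. Lens A ranks best.

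Kruskal–Wallis p = 0.00009. Dunn's z for A against B, with tie correction 567816/(12 × 196) = 241.4, is
(122.48 − 90.26) / √[(197 × 198/12 − 241.4)(1/66 + 1/66)] = 32.22/9.55 = 3.37, Bonferroni p = 0.002. For A against C, p = 0.0002.

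Median (IQR) is 9 (9–10) for A and 8 (8–9) for both B and C, which agrees with the test. So reversal is possible.

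**Step 2: how often, under assumed shapes?** Base case: monofocal 10/9/8 in 25/45/30%; EDOF 10/9/7/5/4 in 62/13/5/10/10%; enhanced monofocal close to monofocal.
- Means and SDs: monofocal 8.95 and 0.74; EDOF 8.62 and 2.19.
- Probability of superiority for EDOF = P(higher) + ½P(tie) = (0.62 × 0.75 + 0.13 × 0.30) + ½(0.62 × 0.25 + 0.13 × 0.45) = 0.504 + 0.107 = 0.611.

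Each case was simulated in 4,000 trials, with Kruskal–Wallis at 0.05 followed by tie-corrected Dunn with Bonferroni × 3. A conflict is a significant Dunn result for EDOF over monofocal together with a lower EDOF sample mean.

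| Assumed shapes | Conflict, share of all trials |
|---|---|
| Base case | about 35–37% (47–49% significant for EDOF) |
| EDOF minority at 4–5 halved to 10%, the rest moved to 9 | about 15% |
| Both comparators also given a 10% minority at 4–5 | about 8% |
| EDOF 10/9/8/7/5/4 in 55/20/10/5/5/5% | about 6% |

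The spread in the base case depends on how close enhanced monofocal is to monofocal.

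**Step 3: and with shift only?** Two exponential groups of 66 that differed by a pure shift were compared by a Mann–Whitney test. The mean pointed against a significant result in 4 of 1,790 tests (0.22%) and 2 of 2,945 (0.07%). Skewness alone therefore does little; a difference in shape is what matters.

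**The case against.** Four points weigh on the other side.

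**The route is not settled.** A reader might infer that the satisfaction scores will be rank-tested. The SAP does not say so. It assigns no named outcome to Kruskal–Wallis, and it allows ANOVA for some binocular outcomes. If satisfaction goes to ANOVA, mean and SD match the test and the point falls away for those outcomes. This stands, and the consequence for the primary outcomes is conditional on it.

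**The large figure is one chosen case.** A reader might infer that over a third of such comparisons would be shown reversed. That rests on a 20% EDOF minority at 4–5 against a monofocal group with nobody below 8, and nothing in the documents supports those shapes. Milder shapes give 6–15%. This stands too: the examples show possibility, not likelihood.

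**A wrong statement needs a further slip.** Dunn's statistic is signed, so the analyst knows which lens ranked higher, and the plan does not tell authors to take direction from the means. In the base case no conflicting trial had a significant Welch difference in means the opposite way, and the SDs (2.19 against 0.74) are a visible warning. This lowers the risk. It does not give the reader an estimate of what was tested.

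**Silence is not a ban.** The section does not forbid other summaries. True, but it is the only rule given for continuous variables, and it covers them all.

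**Conclusion.** The mismatch holds on the text. Any continuous outcome sent to Kruskal–Wallis and Dunn would, under the plan as written, be shown with a summary the test did not examine and with no estimate of the quantity it did.

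Reversed direction is the extreme consequence and needs two conditions: the bounded scores go to the rank test, and the lens groups differ in shape. Under the four assumed sets of shapes at 66/66/65 it occurred in about 6–37% of trials. Those figures are illustrations, not bounds or forecasts. Under shift alone it was about 0.1–0.2% of significant tests. The real likelihood cannot be estimated from the documents.

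A reader might go further and conclude that the rank tests are unsound. They are not: their error rates and validity are untouched, and outcomes analysed by ANOVA are unaffected. This is a minor reporting correction, worth making because it is cheap.

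**What to change.** Amend Descriptive Statistics so that the summary follows the test. For each outcome tested by Kruskal–Wallis and Dunn:
- report median (IQR) alongside mean and SD;
- give one rank-consistent estimate per lens pair with a 95% CI, for example the probability of superiority;
- state the direction of any significant result from the ranks, not from the means.

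The percentage of patients at each score on the 0–10 items would be informative but is optional. Mean and SD can remain the main summary wherever means are tested. It would also help to list which outcomes take the rank route.

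The cost is some SAP wording and a few table columns, computed from data already held.
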